## **6.2.2 Reportable Adverse Events**

- For this protocol, a reportable adverse event includes all events meeting the definition of an adverse event.
- All reportable Adverse Events whether volunteered by the participant, discovered by study

personnel during questioning, or detected through ophthalmological examination, laboratory test,

- or other means will be reported on an adverse event form online.
- 880 The purpose of AE collection for the GYROS study will be to provide historical controls for
- future clinical trials. As a no greater than minimal risk study, AEs do not require any specific
- reporting to regulatory or oversight bodies. However, each Principal Investigator is responsible
- for abiding by any other reporting requirements specific to their IRB or equivalent ethics
- 884 oversight committee

## 6.2.3 Relationship of Adverse Event to Study Procedure

- The study investigator will assess the relationship of any adverse event to be related or unrelated to a study procedure by determining if there is a reasonable possibility that the adverse event may have been caused by the study procedure.
- To ensure consistency of adverse event causality assessments, investigators should apply the
- following general guideline when determining whether an adverse event is related:
- 891 Yes
- 892 There is a plausible temporal relationship between the onset of the adverse event and the study
- procedure, and the adverse event cannot be readily explained by the participant's clinical state,
- intercurrent illness, or concomitant therapies; and/or the adverse event follows a known pattern
- of response to the study procedure; and/or the adverse event abates or resolves upon
- discontinuation of the study procedure.
- 897 **No**
- 898 Evidence exists that the adverse event has an etiology other than the study procedure (e.g.,
- 899 preexisting medical condition, underlying disease, intercurrent illness, or concomitant
- 900 medication); and/or the adverse event has no plausible temporal relationship to study procedure.

## 901 6.2.4 Severity (Intensity) of Adverse Event

A severity assessment is a clinical determination of the intensity of an event. Thus, a severe adverse event is not necessarily serious. For example, itching for several days may be rated as severe, but may not be clinically serious.

- The severity (intensity) of an adverse event will be rated on a three-point scale: (1) mild, (2) moderate, or (3) severe.
- MILD: Usually transient, requires no special treatment, and does not interfere with the participant's daily activities.
- MODERATE: Usually causes a low level of inconvenience, discomfort or concern
   to the participant and may interfere with daily activities but is usually ameliorated by
   simple therapeutic measures and participant is able to continue in study.
- 912
  913 3. SEVERE: Interrupts a participant's usual daily activities and causes severe discomfort.

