## 8496.2 Adverse Events

## **6.2.1 Definitions**

- Adverse Event (AE): Any untoward medical occurrence, including laboratory findings,
- associated with study procedures whether the event is considered related. Progression of GA
- retinal dystrophy including new or worsening of anticipated clinical signs or symptoms, which
- are collected and assessed as unequivocally associated with the disease progression should NOT
- be reported as AEs unless the disease progression is greater than anticipated in the natural course of the disease.
- Serious Adverse Event (SAE): Any untoward medical occurrence that results in any of the
   following outcomes:
- 859 Death.
- A life-threatening adverse event: (a non-life-threatening event which, had it been more severe, might have become life-threatening, is not necessarily considered a serious adverse event).

- Inpatient hospitalization or prolongation of existing hospitalization.
- A persistent or significant disability/incapacity or substantial disruption of the ability to conduct normal life functions.
- A congenital anomaly or birth defect.

An important medical event that may not result in death, be life-threatening, or require

hospitalization may be considered serious when, based upon appropriate medical judgment, they

may jeopardize the patient or subject and may require medical and surgical intervention to
 prevent one of the outcomes listed in this definition.

- 871 **Note:** As this is a Natural History Study, the Investigator(s) will make the categorical
- determinations of Adverse Events, as described above, and will report each determination to the Coordinating Center, as per data collection
- 873 Coordinating Center, as per data collection.

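### The three adverse event severity grades in 6.2.4 leave no fitting grade for painless events that cause major loss of function

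*Protocol*

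**What the plan says.** Protocol section 6.2.4 rates every adverse event on a three-point scale.

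- **Mild:** as a rule short-lived, with no need for special treatment and no effect on what the participant does each day.
- **Moderate:** "Usually causes a low level of inconvenience, discomfort or concern". It may interfere with daily activities, but is usually relieved by "simple therapeutic measures and participant is able to continue in study".
- **Severe:** interrupts "usual daily activities and causes severe discomfort".

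The section opens by stating that "A severity assessment is a clinical determination of the intensity of an event". It keeps severity apart from seriousness, with the example that "itching for several days may be rated as severe, but may not be clinically serious".

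Seriousness is defined in section 6.2.1. One of its criteria is "A persistent or significant disability/incapacity or substantial disruption of the ability to conduct normal life functions"; none of them mentions discomfort. The same section keeps anticipated progression of the retinal dystrophy out of adverse event reporting unless it is greater than expected.

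Section 6.2.2 says why the data are collected: "The purpose of AE collection for the GYROS study will be to provide historical controls for" future trials. Section 1.6 lists consistent adverse event definitions across sites among the measures against bias.

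**The concern.** In a retinal study, some important ocular events may cause little or no discomfort. The top grade nevertheless makes severe discomfort a requirement, alongside interruption of activities. If such an event has no natural place on the scale, each of the roughly twelve sites must decide for itself where to put it.

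What is at stake is the use of the severity grades as an external comparator. A later trial of an ocular treatment may tabulate severe ocular events against this cohort. If the grades here depend on how each site worked around the definition, that comparison mixes a real difference in events with a difference in grading practice.

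**Working it through.** No arithmetic applies. The check is whether the three definitions cover a painless event that stops usual activities and needs more than simple measures. The example is an incident retinal detachment treated by surgery.

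**Is such an event reportable?** Yes. Section 7.1.2 has any condition that could affect an outcome assessment reported as an adverse event. The progression exception in 6.2.1 covers only anticipated worsening of the gyrate atrophy dystrophy. Section 7.2.2 foresees intraocular surgery during the study.

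**Mild?** No. The event needs treatment and interferes with activities, and the definition is not hedged on either of those two elements.

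**Moderate?** Not a fit. The grade describes a low level of inconvenience, discomfort or concern and an event that simple measures usually relieve. Those two elements are hedged, however, and the only firm element is that the participant can continue in the study. A participant with a repaired detachment can normally do so, so a site could still defend this grade.

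**Severe?** Not on the wording. Usual activities are interrupted, but there is no severe discomfort, and both are required. The conjunction does not look like loose drafting: section 6.2.3, immediately before, writes *and/or* three times where alternatives are meant.

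**Result.** No grade describes the event. One investigator can choose moderate because its hedged wording does not rule the event out. Another can choose severe because the rating is a clinical determination. Both have support in the text, so grading may be inconsistent, and where moderate is chosen it is lower than the functional impact suggests.

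**Size.** The protocol gives no expected number of such events and no information on how sites would grade them. The number misgraded cannot be computed from it.

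**The case against.** The strongest reply is that severity is a clinical judgement of intensity, not a mechanical rule, so an investigator is free to grade a disabling painless event as severe. This stands against a stronger reading that some may draw: that such events cannot be graded severe, so that their severe rate is zero by construction and the severity data are wrong. The protocol does not support that reading. Where no definition fits, the outcome is ambiguity, not a forced grade. The reply does not close the gap, though. Events are to be rated on the defined scale, and judgement without a fitting definition is what lets sites diverge.

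A second reply is that clinically important events are caught elsewhere. The seriousness criteria need no discomfort, every event is MedDRA-coded under 6.2.6, and 6.2.7 records outcome, including recovery with sequelae. This also stands: a later trial could compare detachments by coded term and seriousness whatever the grade. But these fields record identity, seriousness and outcome. Section 6.2.4 itself says that severity is a different thing, so they do not repair the grade.

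Third, the set of affected events is narrow. Anticipated progression is not reported, and current vitreous hemorrhage and, at the investigator's judgement, confounding retinal detachment are excluded at screening under 2.3.1.4. What remains is incident painless events other than progression, or progression beyond what is expected. That is accepted, and it rules out the claim that the scale fails for the events that matter most in this study.

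Fourth, Chapter 8 uses no severity grade, and visual function is measured directly at the annual visits. That is accepted too.

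Finally, a reader might take the itching example as a sign that the scale ranks trivial events above sight loss. It is not. It illustrates the difference between severity and seriousness and is sound for that purpose.

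**Conclusion.** The point holds as a minor wording defect. Section 6.2.4 has no fitting grade for painless adverse events with major loss of function, so their grades may vary between sites or be too low. This weakens one part of the data that 6.2.2 intends as historical controls, and it sits badly with the aim of consistent definitions in 1.6.

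The consequence is limited. No objective and no planned estimate of this study changes, and the events themselves remain recorded, coded and open to classification as serious. The effect cannot be quantified from the protocol. The conclusion assumes that at least some such events occur, that some investigators follow the written definitions closely, and that a later trial may want to compare severity grades. The site manual of procedures is not shown and might give further grading guidance.

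**What to change.** In 6.2.4, keep the condition that the event interrupts usual daily activities. Replace the second condition of the severe grade with: *causes severe discomfort, or causes substantial loss of function (including visual function) with or without discomfort*. Repeat the wording wherever site materials restate the grades.

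A bare change from *and* to *and/or* would be worse. Moderate already covers events that may interfere with activities, so the boundary for low-discomfort events would rest on interfering versus interrupting, neither of which is defined. Brief, low-discomfort interruptions could then be graded severe. Requiring interruption together with either severe discomfort or substantial functional loss keeps the boundary clearer.

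The cost is one line of text and a note to sites. A few events may be graded higher than under the present text, and *substantial* still calls for judgement. If events have already been graded, those with functional loss should be looked at once more so that a single scale applies throughout.

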### 914 **6.2.5 Expectedness**

As this is a Natural History Study, the expectedness for a serious adverse event will not be assessed.

### 917 **6.2.6 Coding of Adverse Events**

Adverse events will be coded using the MedDRA dictionary. To facilitate coding, the site will enter a preliminary MedDRA code

- 920 **6.2.7 Outcome of Adverse Event**
- The outcome of each reportable adverse event will be classified by the investigator as follows:
- 922 1. RECOVERED/RESOLVED (COMPLETE RECOVERY) The participant
   923 recovered from the AE/SAE without sequelae. Record the AE/SAE stop date.
- 924
   925
   926
   **2.** RECOVERED/RESOLVED WITH SEQUELAE AE/SAE where the subject recuperated but retained pathological conditions resulting from the prior disease or injury. Record the AE/SAE stop date.
- 927
  928
  928 event that was the cause of death should be reported as fatal. AEs/SAEs that were
  929 ongoing at the time of death; however, were not the cause of death, will be recorded
  930 as "resolved" at the time of death.
- 931
   931 4. ONGOING NOT RECOVERED/NOT RESOLVED An ongoing AE/SAE is defined as an ongoing event with an undetermined outcome.
  - An ongoing outcome will require follow-up by the site to determine the outcome of the AE/SAE.
- The outcome of an ongoing event at the time of death that was not the cause of
  death, will be updated and recorded as "resolved" with the date of death recorded
  as the stop date.

933

934

- 938
   938 **5.** ONGOING (MEDICALLY STABLE) AE/SAE is ongoing, but medically stable.
   939 For example, a chronic condition where no further change is expected.
- If any reported adverse events are ongoing when a participant completes the study (or
- withdraws), they will be followed until they are either resolved, or have no prospect of
- 942 improvement or change, even after the participant has completed all applicable study
- visits/contacts. For all other adverse events, data collection will end at the time the participant
- 944 completes the study.
- Note: participants should continue to receive appropriate medical care for an adverse event after
   their participation in the study ends.
- If a participant is lost to follow up and participant outcome cannot be determined, outcomeclassification will be the last known outcome.

## 949 **6.3 Timing of Event Reporting**

- Investigator(s) are responsible for reporting Adverse Events on the electronic case report form(eCRF) through the study website in a timely manner.
- 952 Each Principal Investigator (PI) is responsible for reporting serious study-related adverse events
- and abiding by any other reporting requirements specific to his/her Institutional Review Board
- (IRB) or Ethics Committee (EC). Where the JCHR IRB is the overseeing IRB, sites must report
- all serious, related adverse events regardless of whether they are expected/anticipated and
- regardless of whether they are fatal or life-threatening within seven (7) calendar days.

957

## 958 Chapter 7: Miscellaneous Considerations

### 959 **7.1 New or ongoing Medical Conditions and Medications**

### 960 **7.1.1 Pre-Existing Condition**

Any medical condition that is either present at screening, a chronic disease, or a prior condition that could impact the participant's health during the study (e.g., prior myocardial infarction or stroke).

### 964 **7.1.2 Medical Conditions during the study**

In addition to conditions meeting the reporting requirements for an adverse event or as described above, the following medical conditions should also be reported: (1) new diagnosis of a chronic disease (i.e., not present at the time of enrollment), and (2) any medical condition that could affect the participant's ability to carry out any aspect of the protocol or could affect an outcome assessment. These will be reported as adverse events. See **Chapter 6.2 Adverse Events** for more detail.

### **7.1.3 Medications**

All medication for the treatment of chronic pre-existing conditions, medical conditions, and/or

adverse events that the participant is currently taking at screening and during the study should be recorded. Nutraceuticals and preventative treatments that are of interest to the study will be

975 recorded.

### 976 **7.2 Prohibited Medications, Treatments, and Procedures**

### 977 **7.2.1 Prohibited Medications and Treatment for** *OAT***-Related Retinal Degeneration**

Participants who are **enrolled into the final study cohort** should not receive IRD treatments during the study. This includes enrolling into an experimental treatment trial of underlying conditions related to *OAT* mutations during the 4-year study duration. However, if the participants enroll in a treatment trial the Executive Committee will be consulted and will

- determine if the participant may continue in the study.
- 983 Examples of prohibited medications and treatments include, but are not limited to the following:
- use of ocular stem cell or gene therapy 984 ocriplasmin 985 ٠ ophthalmic oligonucleotide 986 ٠ Ozurdex (dexamethasone) 987 • Iluvien or 988 Yutiq (fluocinolone acetonide) intravitreal implant 989 ٠ Amiodarone, chloroquine, deferoxamine, hydroxychloroquine, pentosan polysulfate, 990 ٠ tamoxifen, thioridazine 991

## 992 **7.2.2 Intraocular Surgical Procedures**

Participants enrolled into the final study cohort, who have intraocular surgery during the study,
will have follow-up visits timed either before the surgery date or at least three (3) months after
the surgery date. Clinical sites will make reasonable efforts to schedule the participant's follow-

996 up visit as close to the visit target window as possible.

## 997 **7.2.3 Treatment for Cystoid Macular Edema (CME)**

998 Participants enrolled into the final study cohort, who need to receive treatment for CME 999 during the study, may do so with an oral or topical dorzolamide, topical nonsteroidal or

1000 injectable corticosteroid, but not a steroid implant.

### 1001 7.3 Pregnancy Reporting

1002 If a pregnancy occurs, the participant will remain in the study. The occurrence of pregnancy will

1003 be reported to the Coordinating Center within seven (7) days of the site's discovery of the

- 1004 pregnancy (including at screening) and the Pregnancy Notification form will be completed
- 1005 within seven (7) calendar days. Sites will collect concomitant medications throughout the

1006 pregnancy. If an Adverse Event occurs because of the pregnancy, then the site will record the

1007 Adverse Event on the Adverse Event form.

### 1008 7.4 Participant Compensation

1009 Participant compensation will be specified in the informed consent form.

### 1010 7.5 Participant Withdrawal

- 1011 Participation in the study is voluntary, and a participant may withdraw at any time. For
- 1012 participants who withdraw, their data will be used up until the time of withdrawal.

### 1013 **7.6 Confidentiality**

1014 For security and confidentiality purposes, participants will be assigned an identifier that will be

1015 used instead of their name. Protected health information gathered for this study will be shared

1016 with the coordinating center, the Jaeb Center for Health Research in Tampa, FL. De-identified

1017 participant information may also be provided to research sites involved in the study.

## 1018Chapter 8: Statistical Considerations

### 1019 8.1 Statistical and Analytical

1020 The approach to sample size and statistical analyses are summarized below. The analysis plan 1021 synopsis in this chapter contains the framework of the anticipated final analysis plan.

### 1022 **8.2 Sample Size**

The sample size evaluation focuses on objective 1a of the study, to characterize the natural 1023 1024 history of retinal degeneration associated with disease-causing OAT variants in the presence of standard care dietary treatment regimens over four (4) years, using functional, structural, and 1025 1026 patient-reported outcome measures. A justification of the selected sample size using percent 1027 change for the outcomes of interest is outlined. The precision of estimates and of the correlation between structure-based, function-based, and metabolic-based outcomes involved in objective 1028 two (2) and of the correlation between eyes in the outcomes is also provided. Calculations to 1029 1030 address objective three (3), explore risk factors associated with progression (i.e., compare

1031 subgroups for dichotomous risk factors), are summarized.

# 1032 8.2.1 Sample Size Considerations for Evaluating Percent Change from Baseline to four 1033 (4) Years – All Outcomes

1034 Longitudinal changes on all outcome parameters being collected will be examined with the

1035 change in preserved retina being of particular interest. Change from baseline to four (4) years

1036 will be evaluated for sample size purposes, although statistical analyses will include the data

1037 from each annual visit. The power and sample size calculations below may be used to consider

1038 percent change on any outcome measure from baseline to four (4) years.

1039 Both eyes of a participant will be assessed for the main outcomes of interest. Thus, if there are N

1040 participants, 2N eyes will be available for analysis. However, outcome measures from two (2)

1041 eyes of a person are typically strongly correlated ( $r \ge 0.5$ ). The contribution of information from

1042 the two (2) eyes in this case is (2/(1+r)) instead of two (2). Values for the multiplier to the

1043 number of participants to obtain an effective sample size are given below:

r	Effective N
0.0	2.00
0.1	1.82
0.2	1.67
0.3	1.54
0.4	1.43
0.5	1.33
0.6	1.25
0.7	1.18
0.8	1.11

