## 820 **5.2 Questionnaires**

- 821 The following questionnaires will be administered in the study by a certified investigator or
- 822 coordinator. Each questionnaire takes about fifteen (15) minutes to administer.

Questionnaire	Туре	Description	Vision Cohort	Age
Michigan Retinal Degeneration Questionnaire (MRDQ)	Vision Function	The MRDQ is a psychometrically validated patient-reported outcome measure for inherited retinal degenerations questionnaire which consists of fifty-nine (59) questions measuring seven (7) unidimensional domains: central vision, color vision, contrast sensitivity, scotopic function, photopic peripheral vision, mesopic peripheral vision, and photosensitivity.	All	Adults >= 18 years
PROMIS-29® (Patient-Reported Outcomes Measurement Information System®)	Global physical, mental, and social health	The PROMIS®-29 contains items from seven PROMIS domains: depression; anxiety; physical function; pain interference; fatigue; sleep disturbance; and ability to participate in social roles and activities. The seven domains cover the most relevant areas of self- reported health for most people with chronic illness. There is also one 11- point rating scale for pain intensity.	All	Adults >= 18 years
Visual Symptom and Impact Outcomes Patient Reported Outcome (ViSIO-PRO)	Vision Function and HRQoL	The ViSIO-PRO is an instrument designed to assess visual function symptoms, impacts on functional vision, and impacts on wider health- related quality of life (HRQoL). It has been designed for completion by adolescents (12-17) and adults (18 +) with retinitis pigmentosa (RP).	All	Adolescents (12-17) and Adults (18+)
L. V. Prasad- Functional Vision	Vision Function	The LVP-FVQ-II questionnaire consists of twenty-three (23)	All	Children (<18 years)

Questionnaire (LVP-FVQ II)	questions. The questionnaire is used to assess self-reported difficulties in	
	performing daily tasks in children with visual impairment.	

823

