#### If forty (40) study participants or forty-four (44) effective eyes are recruited: 1134

- The half width of a 95% CI around the point estimate for mean percent change would be 1135 six (6) %. 1136
- A comparison of two equal-sized subgroups would have about 80% power to conclude 1137 there is a difference if the true difference is 17%. 1138
- For the objective of evaluating the agreement in outcome between eyes, a sample size of 1139 forty (40) participants for Vision Cohorts 1 and 2 will yield a 95% CI of (0.22,0.70) when 1140 the observed r equals 0.5, and (0.65, 0.89) when the observed r equals 0.8. 1141

For the objective of evaluating the correlation between outcomes, an effective sample size of forty-four (44) participants for Vision Cohorts 1 and 2 will yield a 95% CI of (0.24,0.69) when the observed r equals 0.5, and (0.66,0.89) when the observed r equals 0.8.

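### The two-eye effective sample size (40 participants counted as 44) is offered for every outcome, but it does not apply to outcomes measured once per person, where power at 17 points is about 75–77% rather than about 80%

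*Protocol*

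**What the plan says.** Section 8.2 bases the sample size on objective 1a, which covers functional, structural and patient-reported measures, and continues directly into the justification: "patient-reported outcome measures. A justification of the selected sample size using percent" change. The headings of Sections 8.2.1 and 8.2.2 both claim all outcomes. Section 8.2.1 adds: "The power and sample size calculations below may be used to consider" "percent change on any outcome measure from baseline to four (4) years".

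The next paragraph of 8.2.1 brings in the two-eye argument, beginning "Both eyes of a participant will be assessed for the main outcomes of interest. Thus, if there are N". It gives the information from two correlated eyes as 2/(1+r) and assumes r = 0.8. From there Table 6.1, the worked examples in 8.2.2 and the summary in 8.2.4 all use the effective count: "If forty (40) study participants or forty-four (44) effective eyes are recruited". For that case 8.2.4 states a 95% CI half-width of 6% and about 80% power for a 17% difference between two equal subgroups.

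The visit schedules list the questionnaires under participant-level procedures, separately from the ocular tests done in each eye. In Section 5.2, MRDQ and PROMIS-29 are for "Adults >= 18 years", LVP-FVQ II is for those under 18, and ViSIO-PRO covers ages 12 and over. All four are for all Vision Cohorts. Plasma and blood spot ornithine, the primary metabolic outcomes in the Protocol Summary, come from one sample per person at each collection.

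**The concern.** A second eye adds information only when the outcome is measured in each eye. A questionnaire score or an ornithine level has no second-eye counterpart, so 40 participants are at most 40 observations. The text nevertheless offers one set of figures for every outcome and gives no person-level figure for mean change or subgroup power.

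This matters because the Protocol Summary says the study should show which functional, structural and patient-reported measures are most sensitive to change, and should inform later trial sizing. A reader taking 8.2.4 at face value would credit a questionnaire with the subgroup power of a two-eye measure. Three of the four questionnaires are also limited by age while enrolment starts at 12, so their own n may be below 40. Chapter 8 does not mention this.

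**Working it through.** **Inputs.** Participants: 40 from Vision Cohorts 1 and 2 (8.2.1, 8.2.4). Inter-eye correlation: 0.8 (8.2.1). SD of four-year percent change: 20% (8.2.4). Type I error: 0.05 (8.2.2), taken as two-sided because the text does not say. Two equal subgroups, true difference 17 points (8.2.4).

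**Formulas.** Effective n = N × 2/(1+r). Half-width = 1.96 × SD/√n, or the same with the t quantile on n − 1 degrees of freedom. Power for two groups of n/2: standardised shift = difference / (SD × √(4/n)), then either the normal approximation or the noncentral t with n − 2 degrees of freedom.

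**Step 1: reproduce the protocol.**
- Effective n = 40 × 2/1.8 = 44.4, used as 44.
- Half-width = 1.96 × 20/√44 = 5.9%, printed as 6%.
- Shift = 17/(20 × √(4/44)) = 2.82. Power is 80.5% (normal) or 78.6% (t), in line with the stated figure of about 80%.
- By t, the difference detectable with 80% power is 17.3 points, or 0.86 SD, as printed in 8.2.2.

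The protocol's figures are therefore correct for an outcome measured in both eyes.

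**Step 2: one value per person, n = 40.**
- Half-width = 1.96 × 20/√40 = 6.2% (6.4% by t). Both round to 6%.
- Shift = 17/(20 × √(4/40)) = 2.69. Power is 76.7% (normal) or 74.5% (t).
- Difference detectable with 80% power: 17.7 points (normal) or 18.2 points (t).

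**Step 3: the remaining SDs in the 40-participant column of Table 6.1.** By the normal formula at n = 40, SDs of 30, 40 and 50% give half-widths of 9.3, 12.4 and 15.49%. These round to the printed 9, 12 and 15%, so the column is unchanged.

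**Step 4: count Vision Cohort 3.** Section 2.1 aims for 45 completers and the questionnaires go to all cohorts. With 45 people, t power at 17 points is 79.6%, which meets the stated figure for an outcome collected at all ages.

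**Step 5: age-restricted questionnaires, illustration only.** The protocol gives no split between adults and minors. If 4 or 8 of the 40 were minors, an adult-only instrument would have:

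| Adults | Power at 17 points (t) | Half-width (normal) | Detectable at 80% power (t) |
|---|---|---|---|
| 36 | 70% | 6.5% | 19.2 points |
| 32 | 64% | 6.9% | 20.5 points |

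**The case against.** The best defence is that the text limits itself. The multiplier is introduced on the premise that both eyes are assessed for the main outcomes, 8.2.2 speaks of functional variables and counts eyes, 8.2.4 says effective eyes, and no sentence states 80% power for a questionnaire by name. Ornithine belongs to objective 1b, while 8.2 focuses on 1a. This narrows the reading but does not cancel two headings that claim all outcomes, an explicit offer for any outcome measure, and the naming of patient-reported measures in the objective being sized.

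The other points in defence carry more weight:
- Precision is the protocol's primary criterion, and a reader might infer that the 6% half-width also fails. It does not: at n = 40 it is 6.2–6.4%.
- A reader might infer a large loss of power from the age limits. The protocol supports no specific loss, because the number of minors is not given. The direction is clear if both age groups enrol, but the size is unknown.
- The loss at n = 40 disappears for an outcome collected at all ages if Vision Cohort 3 is counted.
- Table 6.1 prints participant counts beside effective n, spans 10 to 50 participants and is offered for subgroups. The multiplier table includes 1.00 at r = 1.0. A careful reader could find the right value, though the text never links it to person-level outcomes.
- The subgroup comparisons are exploratory, and 8.3.1 already warns of low power with only 40 patients.

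**Conclusion.** The point holds as one of scope, with a modest numerical consequence. The printed figures are right for outcomes measured in both eyes. For an outcome measured once per person in the 40 participants of Vision Cohorts 1 and 2, the stated power of about 80% at 17 points is overstated by roughly 4 percentage points on either method: 78.6% becomes 74.5% by t, and 80.5% becomes 76.7% by the normal approximation. The difference detectable with 80% power rises from about 17 to about 18 points. The stated precision stands after rounding.

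This rests on the protocol's SD of 20%, which comes from a trial in another retinal disease and is not shown to apply to questionnaire scores or ornithine. It also rests on a two-sided test with equal subgroups, on no missing data, and on counting Vision Cohorts 1 and 2 only. With Vision Cohort 3, an all-ages outcome returns to about 80%. The age-restricted questionnaires will fall below 40 if both adults and minors enrol. The illustrative figures above show how power responds to that and are not estimates for this study. Nothing here shows that the study is too small for its purpose.

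**What to change.** In 8.2.1, and in the headings of 8.2.1 and 8.2.2, limit the effective-n figures to ocular outcomes measured in both eyes. Add one sentence: for outcomes measured once per participant, such as questionnaires and ornithine, the multiplier is 1.00 and n is the number of participants providing that outcome.

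In 8.2.4, add a person-level line for n = 40: half-width still 6%, about 75–77% power at 17 points, and 80% power at about 18 points. State whether Vision Cohort 3 is counted; if it is, give the figure for about 45 people instead. Note that MRDQ, PROMIS-29 and LVP-FVQ II should be read at their own smaller n.

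The cost is a few words and one or two lines in Chapter 8. Enrolment, data collection and analysis do not change. The only downside is slightly less favourable stated figures for person-level outcomes.
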